7.3. Follow Up Data Collection

Study participants will be followed up for 3 years or until they withdraw from the study. Follow-up information will be collected at 6-month intervals:

- Regular tests
 - o HBV serology
 - o HBV DNA
 - o Serum creatinine and eGFR [MDRD equation]
 - Serum phosphate
 - Alanine transaminase (ALT) and aspartate transaminase (AST)
- Other tests and procedures
 - o AFP
 - o Hepatic ultrasound
 - Genotype
 - o Bone mineral density

- Liver biopsy
- o Transient elastography (fibrotouch or fibroscan)
- Hepatic ultrasound /computed tomography (CT) /magnetic resonance imaging (MRI)
- Updated CHB treatment details, e.g. any change to regimen or dosage and reason for change
- Comorbidity and concomitant medication review
- Spontaneous AEs if available
- For treatment adherence, it will be evaluated by the treating physician according to the patients' care seeking care, e.g. whether take the medication as prescribed, have you ever discontinued your medications and for how long?
- For participants who discontinue TDF prematurely, duration of treatment and reasons for TDF discontinuation will be recorded, e.g. SAEs, non-SAEs, and insufficient effectiveness.

7.4. Adverse Events and Pregnancy Events Data Collection

As this study takes a naturalistic design and minimizes the level of interventions, only spontaneous AEs will be collected, i.e. all serious and non-serious adverse events (AEs) and pregnancy exposures related to any GSK product (e.g., Viread) will be collected and reported as described in the study-specific pharmacovigilance plan (sPVP). Our special interest is the renal and bone toxicity related to TDF. In routine clinical practice, collecting and reporting spontaneous AEs including pregnancy exposure is the obligation of physicians. Such events will be evaluated and reported by investigators completing the Spontaneous AE Reporting Form for HCPs, Pregnancy Initial Notification Form for HCPs and Pregnancy Outcome Form for HCPs. The study SAP will oversee the spontaneous AE reports to be forwarded by CRO to local safety team who will report to GSK central safety department.

See study Pharmacovigilance Plan (sPVP) for details. sPVP will include the following elements to ensure a comprehensive approach to safety event collection and reporting:

- Supplier pharmacovigilance training
- Investigator and site staff pharmacovigilance training
- Safety-specific roles
- AEs / SAEs and pregnancy exposures collection and reporting processes
- AEs / SAEs and pregnancy exposures collection forms
- Frequency of data review
- Reporting process and timelines

- Interim reports
- Study-specific PVP monitoring process
- Provision of final study report

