- 1. Sociodemographic: a brief baseline survey will be administered to collect a minimal amount of information. Additional study relevant information (only for enrolled patients) will be collected to enable study analyses.
- 2. Laboratory assessments and other clinical assessments: patients will only be monitored according to their physicians' standard practice without additional study-specified interventions and evaluations. Only available assessments will be collected from routine testing/evaluations using electronic approaches.
- 3. Assessments may not be conducted at the exact scheduled time intervals as there will be no intervention for patients' clinical care. Only available assessments will be collected from routine testing/evaluations. The schedule is to remind physicians to collect data regularly.
- 4. Adverse event and pregnancy exposure reporting: only spontaneous AEs/SAEs and pregnancy exposure related to any GSK products will be reported and summarized.
- 5. The baseline assessment filling with grey colure is mandatory and requested for baseline data collection.
- 6. Follow-up data collection period (e.g. months 6, 12, 18, 24, 30, 36) for patients who have started TDF before the entry of study will be anchored to their actual TDF initiation dates.

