6. STUDY POPULATION

TDF-naïve patients with confirmed diagnosis of CHB who newly initiate (Viread) monotherapy or combination therapy for the treatment of CHB will be invited to participate in this study. Those who have already started TDF treatment and meet all the inclusion and exclusion criteria will be also considered eligible. To minimize selection bias, investigators are encouraged to follow their routine clinical practice and consecutively recruit all eligible patients at their practice. More importantly, patients will only be approached for participation after his/her treatment choice has been naturally made between him/her and the physician/investigator (e.g. whether to get treatment or what anti-viral treatment). Willing participants (or their legal guardian) will be asked to voluntarily provide the informed consent to allow their past, current and follow-up medical information to be collected within the study period. For non-enrolled subjects, the reasons for exclusion will be collected whenever possible.

Hospitals and investigators will be selected mainly based on the representativeness of hospital tier, geographic, the research interest of a specific physician to this study, and the potential CHB patient flow. To better understand the real-world practice in Chinese hospitals, we performed a feasibility assessment among infectious disease physicians in 17 hospitals across the country, including 8 Tier 3 Grade A general hospitals, 6 Tier 3 Grade A infectious disease specialized hospitals, and 3 Tier 2 Grade A general hospitals. 11 out of 17 physicians showed interest in this study and the evidence on TDF's effectiveness and safety in real world setting. The majority of interviewed physicians stated that over 50 CHB patients could be recruited in their practice within 3 months.

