6.1. Inclusion Criteria

Participants will be eligible to be included in this study only if all of the following criteria apply:

- 1. Male or female participants aged 12 years and above, at the time of signing the informed consent.
- 2. Participants who are diagnosed with CHB and meet the criterion of antiviral treatment for HBV infection judged by certified physicians.
- 3. Participants who newly initiate TDF ((only including brand TDF, Viread, and generic TDF, Beixin and Naxinde, which passed China generic quality consistency evaluation by Apr. 1 2018) monotherapy or combination therapy for the treatment of CHB by the judge of investigators at the study entry.
- 4. Participants who have already started TDF at the entry of study and will continue to be treated TDF (including brand TDF, Viread, and generic TDF, Beixin and Naxinde which passed China generic quality consistency evaluation by Apr. 01 2018) with essential medical information record and lab test reports available at the initiation of TDF treatment and follow-up visit.

Essential medical information record and lab test reports:

• *At the initiation of TDF treatment:*

- i. TDF treatment detail: TDF dose, brand name, start date;
- ii. Lab test (within +/-4 weeks of TDF treatment initiation): HBV DNA quantification (using high sensitive real-time PCR assays for HBV DNA quantification with lower limit of detection of 20IU/ml), ALT and/or AST, Serum creatinine and Serum phosphate, HBsAg/Anti-HBs and HBeAg/Anti-HBe
- iii. Medical information: CHB diagnosis and treatment history, co-morbidity, concomitant treatment
- The following visits under TDF treatment prior to entry of the study (At least once following visit record if TDF treatment >6 months):
 - i. Lab test: HBV DNA quantification (using high sensitive real-time PCR assays for HBV DNA quantification with lower limit of detection of 20IU/ml), Serum creatinine and Serum phosphate
 - ii. Medical information: co-morbidity, concomitant treatment, TDF treatment information

The proportion of patients who have already started TDF at the study entry will be monitored closely during study recruitment and will be kept less than 10% of the total study population.

- 5. Participants who are able to perform normal activities and seek regular medical care, e.g., willing to regularly perform lab test to monitor the treatment response.

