9.1.2. Sample Size Assumptions

Sample sizes are estimated based on feasibility and precision level achieved as no formal hypothesis will be tested in this study.

The primary objective of this study is to assess the effectiveness of TDF, with one important indicator being the proportion of subjects who achieve the CVR (i.e. HBV-DNA undetectable) at weeks of 48, 96, and 144. To be able to assess the CVR achievement at week 144, a sample size of 2,000 patients will provide a precision of no more than 2.2%, assuming the percentage of patients achieving CVR is 80% and the rate of loss-to-follow-up and discontinuation is 35%. The precision is calculated by the following: precision = $Z_{(1\alpha/2)}$ *SQRT(p*(1-p)/N), where Z is the critical value of normal distribution corresponding to the probability of 1- α /2 (corresponding to (1- α)*100% confidence interval), and p is the percentage of patients achieving CVR. It is half of the width of 95% confidence interval for the point estimate, which means that the lower and upper bounds of the 95% confidence interval for the patient proportion of interest will be within 2.2% of the point estimate (point estimate +/- 2.2%). In addition, there will be approximately a 73% probability of identifying a least one AE with a true AE rate of 0.1%.

For an exploratory purpose, more calculations about the precisions of evaluating the CVR achievement percentage are also provided for difference sub-populations, such as HBeAg positive or Cirrhosis. Assuming HBeAg positive (Cirrhosis) is made of 54.5% (20%) of HBV patients, the percentage of patients achieving CVR is 80% and 3 -year drop-out rate is 35%, a sample size of N=2000 will have 1090 (400) patients in the interested group and about 708 (260) completers and a precision of no more than 0.029 (0.049) [You, 2016].

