9.2. Populations for Analyses

The main population for analyses will consist of all consented participants who have the requested baseline data and at least one post-baseline assessment data.

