9.3.4.4. Spontaneous Adverse Events and Pregnancy Events

• Spontaneous AEs/SAEs will be summarized using descriptive statistics.

Adverse events will be assigned preferred terms and categorized into body systems according to the medical dictionary for regulatory activities (MedDRA) classification of the World Health Organisation terminology.

The proportion of subjects who experienced AEs will be calculated by dividing the number of subjects who experienced the AE during the treatment period by the number of subjects evaluable for safety analysis. Adverse events will be summarised by treatment group, and by body system and event within each body system. The following summaries of AEs will be provided:

All AEs.

All treatment related AEs.

All SAEs.

All treatment related SAEs.

All AEs leading to permanent discontinuation of study drug.

All AEs leading to permanent discontinuation from the study.

- Pregnancy events will be summarized using descriptive statistics. In addition, change from baseline of serum phosphate, serum creatinine, and creatinine clearance will also be summarized to evaluate the drug safety.
- The incidence of decompensated cirrhosis/liver disease and related complications, such as HCC, will be calculated for weeks of 48, 98 and 144, for the overall analysis population, and for certain sub-populations of interests, such as elderly and baseline Cirrhosis patients

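### AE collection is limited to events related to GSK products, but the AE denominator is not, so reported TDF-related AE proportions run low in line with the generic share, and the 73% detection figure rests on full capture that the collection rule does not support

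*Protocol*

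**What the plan says.** **Collection.** Protocol Section 7.4 confines the safety data to spontaneous reports: "all serious and non-serious adverse events (AEs) and pregnancy exposures related to any GSK product (e.g., Viread) will be collected". Footnote 4 to the Schedule of Activities (Section 2) applies the same limit to reporting: "only spontaneous AEs/SAEs and pregnancy exposure related to any GSK products will be reported and summarized". Table 2 in Section 4 also frames the AE summary by GSK product.

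**Population.** Section 6.1 defines eligible TDF as "only including brand TDF, Viread, and generic TDF, Beixin and Naxinde". It sets no cap and no expected share for the generics. The opening of Section 6, by contrast, describes TDF-naïve patients "who newly initiate (Viread) monotherapy or combination therapy for the treatment of CHB".

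**Denominator.** Section 9.3.4.4 obtains the AE proportion by "dividing the number of subjects who experienced the AE during the treatment period by the number of subjects evaluable for safety analysis". It places no brand limit on that set. The only analysis population the protocol defines (Section 9.2) is "all consented participants who have the requested baseline data and at least one post-baseline assessment data", which includes generic users. Section 9.3.4.4 tabulates AEs by treatment group, and Section 5.3 treats all 2,000 patients as one treatment group.

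**Detection claim.** Section 9.1.2 says the sample gives "approximately a 73% probability of identifying a least one AE with a true AE rate of 0.1" per cent.

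**The concern.** A TDF-related event in a patient on Beixin or Naxinde is not related to a GSK product, so it falls outside the collection rule. Nothing in Section 9.3.4.4 removes that patient from the denominator. The resulting figure would be read as the proportion of TDF patients with the event, yet part of the denominator could not contribute a TDF-related event.

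Section 7.4 gives TDF-related renal and bone toxicity as the special interest, and Section 3.2 gives physicians' safety concerns about TDF as a reason for the study. An AE proportion that is low by construction, next to a stated 73% chance of seeing a rare event, invites too much reassurance when few or no events are reported.

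The all-AE tables in Section 9.3.4.4 carry a related labelling problem. Collection is already filtered on relatedness to a GSK product, so those tables cannot show all AEs.

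**Working it through.** **Inputs from the protocol**
- Enrolled: 2,000 (Section 5.2).
- Loss to follow-up and discontinuation: 35% (Section 9.1.2), leaving 2,000 × 0.65 = 1,300 completers (Table 3).
- True AE rate p = 0.1% and stated detection probability of about 73% (Section 9.1.2).

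**Assumed input.** The Viread share s is not in the protocol. The range shown is 30% to 100%. Generic users are taken to contribute no TDF-related AE, and capture among Viread users is taken as complete.

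**Step 1: reproduce the plan's figure.** P(at least one event) = 1 − (1 − p)^n.
- n = 1,300: 1 − 0.999^1300 = 72.8%, which matches the stated 73%.
- n = 2,000: 1 − 0.999^2000 = 86.5%, which does not.

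The stated figure therefore counts every completer, whatever the brand, and treats every event as recorded.

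**Step 2: apply the collection rule.** Replace n by n × s. With equal true rates by brand, the reported proportion is s × p.

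| Viread share s | 1 − 0.999^(1300s) | 1 − 0.999^(2000s) | Reported proportion if the true one is 0.1% |
|---|---|---|---|
| 100% | 72.8% | 86.5% | 0.10% |
| 90% | 69.0% | 83.5% | 0.09% |
| 70% | 59.8% | 75.4% | 0.07% |
| 50% | 47.8% | 63.2% | 0.05% |
| 30% | 32.3% | 45.1% | 0.03% |

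**Step 3: find where the 2,000 basis drops below 73%.** Solve 1 − 0.999^(2000s) = 0.73. Then s = ln(0.27) / (2000 × ln(0.999)) = 0.654, or about 65%.

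**Reading the two bases.** The 1,300 basis is the protocol's own, but it ignores events reported by patients before they leave. The 2,000 basis is generous, because patients who leave early contribute only part of the follow-up. Incomplete spontaneous reporting among Viread users would lower both columns. The protocol gives no reporting rate, so no figure is put on this.

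**The case against.** The strongest reply has four parts.

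- **Renal and bone safety does not rest on the AE tables.** This stands. Creatinine, eGFR and serum phosphate are central-laboratory tests with no brand limit (Sections 7 and 7.2). Section 9.3.3 analyses them in the overall population, and BMD, where available, is analysed overall (Section 9.3.4.1). Reasons for stopping TDF are recorded without regard to brand (Section 7.3). A reader might infer that generic users' renal and bone signals are lost, but only their reported AEs and SAEs are.
- **The safety set is not defined, and Table 2 speaks of GSK products, so a Viread-only denominator is possible.** This stands in part. That generic users are in the denominator is an inference, though it is the natural reading of Sections 9.2 and 9.3.4.4 together. A later analysis plan could settle the denominator. It could not recover events the protocol never collects, or correct the protocol's 73%.
- **The 73% may still be reached.** This stands. A reader might conclude that the study fails to deliver it. The protocol gives no generic share, and on 2,000 enrolled with full capture the figure holds down to a Viread share of about 65%.
- **Limited collection is a declared choice in a naturalistic, descriptive study, and AE summaries are exploratory.** This stands and lowers the severity. It does not justify dividing a restricted numerator by an unrestricted denominator.

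Three further inferences go beyond the text. The Viread share is not a strict ceiling on the ratio of reported to true proportion: if Viread users had higher true rates, the ratio would exceed it. Generic users taking another GSK product could also contribute events, so the all-AE and treatment-related tables need not coincide. Finally, the Viread wording in Section 6 conflicts with Section 6.1, but the protocol does not show how that arose.

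**Conclusion.** The point holds at moderate severity. As written, the numerator is limited to GSK-product-related events and the denominator has no brand limit. If any generic users are enrolled, TDF-related AE proportions are biased downward. With equal true rates by brand and full capture among Viread users, the reported proportion is the true one times the Viread share, for example half at an assumed share of 50%.

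The 73% is unsupported as stated, rather than shown to be wrong. It requires every event to be captured in 1,300 completers of any brand, and Section 7.4 does not provide for that. Whether the real probability is above or below 73% depends on the Viread share, the patient basis and the completeness of reporting. The protocol gives neither the share nor the completeness.

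**What to change.** 1. **Match numerator and denominator.** Define the AE denominator in Section 9.3.4.4 as patients exposed to Viread, and label the results as spontaneous-report proportions. Section 7.2 already records the brand, so this costs wording only. Alternatively, collect TDF-related AEs for all eligible brands and report them by brand. That adds modest form completion at sites.
2. **Restate or delete the 73%.** If it is kept, give the number of patients it rests on and say that it assumes every event is captured: 1 − 0.999^n for n patients whose events are within the collection rule.
3. **Relabel the all-AE tables** as *all reported GSK-product-related AEs*, with the same change for SAEs, unless collection is widened. Any widened collection needs its own accurate label.
4. **Reconcile the Viread wording** at the start of Section 6 with the brands listed in Section 6.1.

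Items 2 to 4 are text changes only.

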8. DISCONTINUATION CRITERIA

8.1. Discontinuation of Study Treatment

Not applicable. No investigational treatment will be tested.

8.2. Withdrawal from the Study

A participant may withdraw from the study at any time at his/her own request, or may be withdrawn at any time at the discretion of the investigator for safety, behavioral, compliance or administrative reasons. If the participant withdraws consent for disclosure of future information, the sponsor may retain and continue to use any data collected before such a withdrawal of consent.

In this real-world study, participants will be considered withdrawal from the study if any of the following events occurs within the 3-year study period:

Discontinuation of TDF (Viread, Beixin or Naxinde) for at least 28 days

Participation in clinical trials for any new drugs not limited to CHB-related ones during the 3-year study period

Study closed/terminated

Withdrew consent

The overall duration of TDF treatment and the reason for discontinuation of TDF treatment will be collected and the patient's adherence will be evaluated by the investigator a designed questionnaire.

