9.3.3. Secondary Analyses

Patients' renal functional change during TDF treatment period will be explored.

- The proportion of patients whose eGFR (MDRD equation) decline >20% from baseline at weeks of 48, 96 and up to week 144 will be summarized for the overall study analysis population and sub-group populations.
- Mean and 95% confidence intervals for the change from baseline in eGFR values will be calculated for the overall analysis population, as well as for the subpopulations of interests. A mixed effect model will be fitted to explore the impacts on the mean change from baseline in eGFR of fixed effects of age, gender, treatment-naïve or experienced, ADV or non-ADV, type of baseline comorbidities (Cirrhosis, Hypertension, diabetes mellitus (DM), non-overlapping), baseline eGFR values, baseline HBV-DNA counts, baseline HBeAg status, and other factors as appropriate, and random effects of subject ID.
- The percentage of change from baseline in eGFR will be estimated for the overall analysis population and by sub-populations at weeks 48, 96, and 144. Figures of mean eGFR values overall and the sub-populations of interests will be generated.
- The proportion of patients with confirmed a serum phosphate Grade 3 or 4 abnormality (<2.0 mg/dL) at weeks of 48, 98 and 144 will be summarized for the overall study analysis population and sub-group populations.
- The percentage of change from baseline in serum phosphate will be estimated for the overall analysis population and by sub-populations at weeks 48, 96, and 144. Figures of mean serum phosphate values overall and the sub-populations of interests will be generated.
- Mean and 95% confidence intervals for the change from baseline in serum phosphate values will be calculated for the overall analysis population, as well as for the sub-populations of interests. A mixed effect model will be fitted to explore the impacts on the mean change from baseline in serum phosphate of fixed effects of age, gender, treatment-naïve or experienced, ADV or non-ADV, type of baseline co-morbidities (Cirrhosis, Hypertension, DM, non-overlapping), baseline eGFR values, baseline HBV-DNA counts, baseline HBeAg status, baseline phosphorus and other factors as appropriate, and random effects of subject ID.

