9.3.5. Other Analyses

Missing data is inevitable in this real-world study and can have an impact upon the interpretation of the data. In general, values for missing data will not be imputed unless otherwise specified. As this study takes a naturalistic approach, there will be no protocoldictated interventions or approaches to improve patient compliance besides what physicians do in practice. The study will use innovative electronic data capture approaches to increase the efficiency of data collection and reduce the effort on patients, physicians and sites, hopefully to reduce the chance of missing data.

The duration of patients on TDF, the reason for discontinuation if possible, and patients' adherence will be evaluated and recorded. Missing data issue will be explored in data analyses. For example, the reason and occurrence time of missing data will be summarized. It might be informative to know more the missing data and improve the adherence of treatment in the future.

When applicable, additional analyses may be conducted on primary, secondary, and exploratory objectives and research questions and will be described in RAP.

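### A 28-day stop of TDF ends follow-up, so week-144 results based on patients with data would describe those who stayed on TDF

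*Protocol*

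**What the plan says.** Protocol Section 8.2 lists the events that make a participant a withdrawal. One is "Discontinuation of TDF (Viread, Beixin or Naxinde) for at least 28 days". Section 8.1, on discontinuing treatment, is marked as not applicable, so the protocol has no status for a patient who has stopped TDF but remains in the study.

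Section 7.3 sets the length of follow-up: "Study participants will be followed up for 3 years or until they withdraw from the study". The opening of Section 7 says the same. For patients who stop early, Sections 7.3 and 8.2 provide for the duration of TDF, the reason for stopping and an adherence evaluation. They describe no later HBV DNA, creatinine, phosphate or liver outcome. Section 7.3 gives examples of the reasons: "reasons for TDF discontinuation will be recorded, e.g. SAEs, non-SAEs, and insufficient effectiveness".

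On missing data, Section 9.3.5 says: "In general, values for missing data will not be imputed unless otherwise specified". The main population in Section 9.2 is consented participants who "have the requested baseline data and at least one post-baseline assessment data". Section 9.3.2 reports CVR at weeks 48, 96 and 144, and the denominator at each week is not stated. Section 9.3.3 words the eGFR endpoint as "decline >20% from baseline at weeks of 48, 96 and up to week 144", while the phosphate proportion is tied to fixed weeks.

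**The concern.** Read together, these sections make stopping the drug the same event as leaving the study, and some listed reasons for stopping are lack of effect and harm. A patient who fails virologically or loses renal function and therefore stops TDF would contribute no week-144 value. The patients left at week 144 would then be those in whom TDF worked and was tolerated.

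Long-term effectiveness and renal safety are the two questions that Section 3.2 gives as the purpose of the study. That section also criticises registration trials for enrolling patients with better adherence; a completer result would bring back a similar selection. The incidence of decompensation and related complications (Section 9.3.4.4) would be cut off at the TDF stop too. The limitations in Section 12 do not mention this.

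An analysis plan can choose denominators and sensitivity analyses, but it cannot recover results that were never collected. That part belongs in the protocol.

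**Working it through.** **Inputs from the Protocol.** Section 9.1.2: 2,000 enrolled, CVR 80%, 35% lost or discontinued, half-width 2.2%, and 73% probability of seeing an adverse event with a true rate of 0.1%. Table 3 (Section 9.1.3): 1,300 completers.

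**Step 1: reproduce the stated precision.**
- n = 2,000 × (1 − 0.35) = 1,300.
- Half-width = 1.96 × √(0.80 × 0.20 / 1,300) = 0.0217, stated as 0.022.
- With n = 2,000 it would be 1.96 × √(0.16 / 2,000) = 0.0175.
- Adverse event detection: 1 − 0.999^1,300 = 72.8%, matching the stated 73%. With n = 2,000 it would be 86.5%.

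The arithmetic is correct. It shows that the planning denominator is completers.

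**Step 2: CVR over all who started, if 80% is seen in the 65% observed.** Let q be the CVR in the other 35%; the protocol does not give it. Overall CVR = 0.65 × 0.80 + 0.35 × q = 0.52 + 0.35q.

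| q (assumed) | Overall CVR | Gap from 80% |
|---|---|---|
| 100% | 87.0% | −7.0 points |
| 80% | 80.0% | 0 |
| 70% | 76.5% | 3.5 points |
| 50% | 69.5% | 10.5 points |
| 0% | 52.0% | 28.0 points |

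The gap is 0.35 × (0.80 − q). It exceeds 0.0217 once q is below 0.80 − 0.0217 / 0.35 = 0.738.

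**Step 3: allow for the mixture in the 35%.** The protocol does not split discontinuation from loss to follow-up. Suppose that 10% of enrolled patients stop TDF and that the other losses resemble the rest (both assumed). Overall CVR = (0.52 + 0.10q) / 0.75.
- q = 0: 69.3%, a gap of 10.7 points.
- q = 50%: 76.0%, a gap of 4.0 points.
- q = 70%: 78.7%, a gap of 1.3 points, inside the quoted precision.

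**Step 4: a fixed-week renal proportion, all rates assumed.** With the event in 5% of completers and 20% of those who left, the whole-cohort rate is 0.65 × 5% + 0.35 × 20% = 10.25%, so completers understate it by 5.25 points. With equal rates there is no gap. With 10% in completers and 5% in leavers the whole-cohort rate is 8.25%, and the sign reverses.

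**The case against.** The strongest reply is that the protocol never says stoppers leave the week-144 denominator. Section 9.2 needs only one post-baseline assessment, and Section 9.3.2 speaks of the overall analysis population. If stoppers stayed in as not achieving CVR, the result would not be overstated. This stands: upward bias is conditional on the completer denominator, which only the precision calculation points to.

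Second, an on-treatment description may be what is wanted. The renal objective is worded as change during TDF treatment, and HBV DNA after a switch to another antiviral does not measure TDF. This is fair, but the result should then be labelled on-treatment. The primary objective concerns patients who receive TDF in the real world and does not carry the same limit.

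Third, non-responder rules, weighting and bounds are normally left to the analysis plan, and Section 9.3.5 allows exceptions. This stands for the analysis details, so their absence here is not the point. It does not stand for data collection after a stop.

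Fourth, Sections 9.3.4.3 and 9.3.5 compare continuers with discontinuers and summarise the reasons for and timing of missing data. That describes the selection without correcting it.

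Four stronger readings are tempting and are not supported:
- **That 52% to 87% measures the effect of the 28-day rule.** The 35% includes ordinary loss to follow-up, so these are extreme bounds for all missing patients.
- **That every renal result is understated.** The eGFR wording reaching up to week 144 may count declines before the stop, and the mixed models can use earlier values.
- **That the earliest stoppers disappear from every analysis.** Section 9.3.4.3 names no population, and Section 9.3.4.4 has its own denominator of subjects evaluable for safety.
- **That the direction is established.** The reasons in Section 7.3 are examples only; stops for cost, pregnancy or success could weaken or reverse it for some endpoints.

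**Conclusion.** The point holds in conditional form. The withdrawal rule, the end of data collection and the general absence of imputation are explicit. If week-144 CVR is taken over patients with week-144 data, it describes patients who stayed on TDF and is likely to overstate effectiveness among all who started. The fixed-week phosphate proportion is likely to understate harm; the eGFR proportion and the mixed models are less affected.

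The size cannot be derived from the protocol. Under the assumed 70% or 50% CVR in the missing 35%, the gap is 3.5 or 10.5 points, larger than the 2.2 points quoted as precision. With few stoppers who do nearly as well as completers, it can fall below that (1.3 points in Step 3). It needs settling while follow-up data can still be collected.

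**What to change.** 1. In Section 8.2, separate stopping TDF from leaving the study. Unless consent is withdrawn, keep collecting routinely available results to month 36, with no mandated visits or tests. Section 7.3 already records changes of regimen, so later values can be marked as off TDF. No treatment decision changes.
2. State the denominator for CVR at week 144. Label the completer result as on-treatment. Beside it, report CVR over the analysis population with TDF stops for insufficient effectiveness counted as not achieved, and give bounds for the other missing patients. Whether to weight for loss, or to score stops for adverse events as CVR failures, is debatable and can be left to the analysis plan.
3. Report the cumulative proportion with a first on-treatment eGFR decline above 20%, and with phosphate below 2.0 mg/dL, by weeks 48, 96 and 144, using all values before the stop.
4. State that discontinuation and safety summaries use all enrolled patients.

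The cost is a revision of Section 8.2 with matching wording in Sections 7 and 7.3, modest extra data collection and a few added tables. The headline CVR may be less favourable.
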